### 3. DESCRIPTION OF DESIGN AND TRIAL POPULATION

#### 3.1 OVERALL TRIAL DESIGN AND PLAN

The study will be performed as a randomised, open-label, single-dose, incomplete blocks crossover trial in healthy male subjects in order to compare the test treatments TF2 in fasted state (C and E) to the reference treatment TF1 in fed state (A) to investigate the relative bioavailability of tablet formulation. Additionally, it will evaluate the food effect on test treatments. The test treatments will be one single dose of 100 mg BI 1358894 of the TF2 in a fed state (B) and in the fasted state (C) and TF2 in the fed state (D) and in the fasted state (E). The reference treatment to compare the bioavailability of tablet formulations will be one single dose of 100 mg BI 1358894 of the TF1 (A) administered to subjects in the fed state.

Twenty-four subjects will be randomly allocated to 12 treatment sequences. For details, refer to [Section 4.1](#).

The planned 24 subjects to be included in the study will be assigned to three cohorts, each consisting of eight subjects. The cohorts will be treated at least one week apart. The second and third cohort will be dosed after a careful review by the Investigator of the safety data from all subjects in the preceding cohort(s).

Table 3.1: Treatment sequences

Blocks/Sequences	1	2	3	4	5	6	7	8	9	10	11	12
Period 1	A	D	E	C	A	E	B	C	B	D	C	A
Period 2	B	A	B	A	E	D	C	E	D	C	B	E
Period 3	C	B	A	D	C	A	D	B	E	E	A	D

There will be a washout period of at least 17 days between the treatments, i.e. the dose in the first treatment period and the dose in the second treatment period are separated by at least 17 days. In each subject, an assessment of safety laboratory, vital signs, ECG and AEs will be conducted on the last day of the preceding period prior to next dosing. These data will be reviewed by the Investigator to confirm the eligibility of the subject before the following dosing.

An overview of all relevant trial activities is provided in the [Flow Chart](#). For visit schedule and details of trial procedures at selected visits, refer to [Sections 6.1](#) and [6.2](#), respectively.

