#### 4.1.4 Drug assignment and administration of doses for each subject

This trial is an incomplete blocks crossover study. All subjects will receive three out of the five treatments in randomised order. The treatments to be evaluated are outlined in [Table 4.1.4: 1](#) below.

Table 4.1.4: 1 Dosage and treatment schedule

Treatment	Substance	Formulation	Unit strength	Dosage	Total dose
B (Test)	BI 1358894	Tablet	50 mg	2 tablets (50 mg), single dose, fed	100 mg
C (Test)	BI 1358894	Tablet	50 mg	2 tablets (50 mg), single dose, fasted	100 mg
D (Test)	BI 1358894	Tablet	50 mg	2 tablets (50 mg), single dose, fed	100 mg
E (Test)	BI 1358894	Tablet	50 mg	2 tablets (50 mg), single dose, fasted	100 mg
A (Reference)	BI 1358894	Tablet	100 mg	1 tablet (100 mg), single dose, fed	100 mg

Administration of trial medication will be performed after subjects have fasted overnight; fasting is to start no later than 10 h before the scheduled dosing. The investigator (or authorised designee) will administer the trial medication as an oral dose together with about 240 mL of water to subjects who are in a sitting position. For drug administration, the so-called four-eye principle (two-person rule) should be applied. For this, one authorised employee of the trial site should witness the administration of trial medication, and – if applicable – its preparation (e.g. reconstitution), if correct dosage cannot be ensured otherwise.

In three out of the five treatment periods (treatment A, B and D), a high-fat, high-calorie meal will be served 30 min before drug administration. The subjects must completely consume the meal prior to drug intake. The composition of the standard high-fat, high-calorie meal is detailed in [Table 4.1.4: 2](#); this meal is in compliance with the FDA guidance ‘Food-Effect Bioavailability and Fed Bioequivalence Studies’ [[R03-2269](#)]. For restrictions with regard to diet, see [Section 4.2.2.2](#).

Proprietary confidential information © 2019 Boehringer Ingelheim International GmbH or one or more of its affiliated companies

Table 4.1.4: 2

Composition of the high-fat, high-calorie meal

Ingredients	kcal
2 chicken eggs (whole content) for scrambled eggs	192
10 g butter for frying scrambled eggs	75
35 g fried bacon	186
2 toasted slices of wheat bread	130
15 g butter for buttering toast slices	113
115 g hash brown potatoes	132
240 mL whole milk (3.5% fat)	156
Sum^1	984

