### **4.2 OTHER TREATMENTS, EMERGENCY PROCEDURES, RESTRICTIONS**

#### **4.2.1 Other treatments and emergency procedures**

In case of adverse events in need of treatment, the investigator can authorise symptomatic therapy.

In case of alterations of blood pressure (hypotension) and heart rate (tachycardia), which were reported in nonclinical toxicology studies (see [Section 1.2.1.3](#)), first physical

Proprietary confidential information © 2019 Boehringer Ingelheim International GmbH or one or more of its affiliated companies

interventions will be the treatment of symptoms. If unsuccessful, appropriate drug therapy will be initiated according to common guidelines and algorithms of emergency trainings. Dependent on individual symptoms, for the treatment of tachycardia this may include intravenous administration of beta blockers or appropriate antiarrhythmic drugs. For the treatment of hypotension, in addition to volume substitution, administration of vasopressors may be a further step. The entire staff of the trial site assuming medical responsibility during the conduct of the study is routinely trained in emergency procedures.

If required, any subject with an adverse event in need of treatment will be kept under supervision at the trial site or transferred to a hospital until all medical evaluation results have returned to an acceptable level.

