#### 4.2.2 Restrictions

##### 4.2.2.1 Restrictions regarding concomitant treatment

In principle, no concomitant therapy is allowed. All concomitant or rescue therapies will be recorded (including time of intake on study days) on the appropriate pages of the CRF.

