Proprietary confidential information © 2019 Boehringer Ingelheim International GmbH or one or more of its affiliated companies

Previous and concomitant therapies will be presented per treatment group without consideration of time intervals and treatment periods.

Laboratory data will be compared to their reference ranges. Values outside the reference range as well as values defined as possibly clinically significant will be highlighted in the listings. Additionally, differences from baseline will be evaluated.

Vital signs or other safety-relevant data will be assessed with regard to possible on-treatment changes from baseline.

Relevant ECG findings will be reported as AEs.

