### 8.3.1 Source documents

In accordance with regulatory requirements, the investigator should prepare and maintain adequate and accurate source documents and trial records for each trial subject that include all observations and other data pertinent to the investigation. Source data as well as reported data should follow the 'ALCOA principles' and be attributable, legible, contemporaneous, original, and accurate. Changes to the data should be traceable (audit trail).

Data reported on the CRF must be consistent with the source data or the discrepancies must be explained.

Before providing any copy of subjects' source documents to the sponsor, the investigator must ensure that all subject identifiers (e.g., subject's name, initials, address, phone number, and social security number) have properly been removed or redacted to ensure subject confidentiality.

If the subject is not compliant with the protocol, any corrective action (e.g. re-training) must be documented in the subject file.

For the CRF, data must be derived from source documents, for example:

- Subject identification: sex, year of birth (in accordance with local laws and regulations)
- Subject participation in the trial (substance, trial number, subject number, date subject was informed)
- Dates of subject's visits, including dispensing of trial medication

Proprietary confidential information © 2019 Boehringer Ingelheim International GmbH or one or more of its affiliated companies

- Medical history (including trial indication and concomitant diseases, if applicable)
- Medication history
- AEs and outcome events (onset date [mandatory], and end date [if available])
- SAEs (onset date [mandatory], and end date [if available])
- Concomitant therapy (start date, changes)
- Originals or copies of laboratory results and other imaging or testing results, with proper documented medical evaluation (in validated electronic format, if available)
- ECG results (original or copies of printouts)
- Completion of subject's participation in the trial (end date; in case of premature discontinuation, document the reason for it, if known)

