7.2 CONCOMITANT DISEASES AND MEDICATION

Concomitant diseases will be coded according to the most recent version of MedDRA. Concomitant medication will be coded according to the most recent version of the World Health Organisation – Drug Dictionary. Concomitant non-drug therapies will be coded according to the most recent version of MedDRA.

Only descriptive statistics are planned for this section of the CTR.

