The frequency of subjects with AEs will be summarised by treatment, primary SOC and preferred term. AEs which were considered by the investigator to be drug related will be summarised separately. Separate tables will also be provided for subjects with SAEs, subjects with AESIs and subjects with other significant AEs (according to ICH E3 (8)). The frequency of subjects with AEs and the frequency of subjects with AEs considered by the investigator to be drug related will also be summarised by maximum intensity, primary SOC and preferred term.

The SOCs and preferred terms within SOCs will be sorted by descending frequency over all treatment groups.

For disclosure of AE data on ClinicalTrials.gov, the frequency of subjects with non-serious AEs occurring with an incidence of greater than 5 % (in preferred terms) will be summarised by treatment, primary SOC and preferred term. The frequency of subjects with SAEs will also be summarised.

For disclosure of AE data in the EudraCT register, the frequency of AEs, the frequency of non-serious AEs with an incidence of greater than 5 % (in preferred terms) and the frequency of SAEs will be summarized.

For support of lay summaries, the frequency of subjects with drug-related SAEs will be summarized by treatment, primary SOC and preferred term.

If the subject reports headaches during the treatment period further information about the duration of headache, location, characteristics, and signs and symptoms were recorded. The information will be summarized with descriptive statistics.

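### The planned summary of concomitant therapy ignores treatment periods, so in this crossover it cannot show use by formulation and food state; this is a low-severity reporting correction

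*Protocol*

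**What the plan says.** Protocol 7.3.4 gives an explicit rule: "Previous and concomitant therapies will be presented per treatment group without consideration of time intervals and treatment periods". SAP 7.2 covers coding and then says "Only descriptive statistics are planned for this section of the CTR", with no rule for assigning a therapy to a treatment or period. SAP Section 4 records one departure from the protocol, on AEs that occur after the residual effect period, and declares everything else in line with the protocol. The rule in 7.3.4 therefore stands.

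The design is a crossover. Protocol 4.1.4: "All subjects will receive three out of the five treatments in randomised order". Protocol 3.1: "Twenty-four subjects will be randomly allocated to 12 treatment sequences".

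Symptomatic treatment is foreseen. Protocol 4.2.1: "In case of adverse events in need of treatment, the investigator can authorise symptomatic therapy". Its timing is collected. Protocol 4.2.2.1: "All concomitant or rescue therapies will be recorded (including time of intake on study days) on the appropriate pages of the CRF". Protocol 8.3.1 lists start date and changes among the source data for concomitant therapy.

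**The concern.** The rule reads as if written for a parallel-group trial, where a subject belongs to one group throughout. Here a subject belongs to three treatments in turn, and the time information that the rule discards is what identifies the treatment.

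It also sits awkwardly with the rest of the safety plan. Protocol 7.3.4 bases all safety analyses on the treatment actually given at onset and says treatments will be compared descriptively. SAP Table 6.1: 2 defines on-treatment phases for AEs, laboratory data and vital signs. Concomitant therapy is left out of that scheme.

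What is at stake is one tolerability description. Headache was the commonest AE in the earlier food-effect part, reported by 15 of 20 subjects (Protocol 1.2.1.5). How often it or another event led to symptomatic therapy under each formulation and food state is a reasonable thing for this trial to report, and the planned table cannot report it.

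**Working it through.** The plan gives no figure to reproduce. The check is to see what a period-free table can show under the sequences of Protocol Table 3.1.

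**Exposure counts.** There are 12 sequences with 2 subjects each. Treatment A appears in 8 sequences (16 subjects); B, C, D and E appear in 7 each (14 subjects). The total is 16 + 4 × 14 = 72 subject-treatment exposures, which is 24 × 3. A, B and D are fed; C and E are fasted. Eight sequences have two fed periods and one fasted, three have one fed and two fasted, and one (D-A-B) is all fed. So 11 of 12 mix food states.

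**Reading 1: treatment group means treatment.** With periods ignored, a tablet taken once, in one period, is counted in three of the five columns.

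**Reading 2: treatment group means sequence.** The table has 12 columns of two subjects, each column covering three treatments. No column stands for one formulation and food state.

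**Illustration of the dilution, Reading 1 only.** The headache rates at 100 mg in Protocol Table 1.2.1.5: 2 are 7/12 fasted and 4/12 fed. Assume these rates apply to every fasted and fed treatment here, that periods are independent, and that a share *s* of headaches is treated. True use is p = s × 7/12 (fasted) or s × 4/12 (fed). The period-free column for a treatment is the mean of 1 − (1 − p₁)(1 − p₂)(1 − p₃) over the sequences that contain it.

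For s = 1, the any-time probabilities by type of sequence are:
- three fed: 1 − (8/12)³ = 0.704
- two fed, one fasted: 1 − (8/12)²(5/12) = 0.815
- one fed, two fasted: 1 − (8/12)(5/12)² = 0.884

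Column C (four sequences of the second type, three of the third): (4 × 0.815 + 3 × 0.884)/7 = 0.845. Column E has the same make-up. Column A (one, six and one of the three types): (0.704 + 6 × 0.815 + 0.884)/8 = 0.810. Columns B and D (one, five and one): (0.704 + 5 × 0.815 + 0.884)/7 = 0.809.

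| Share treated (assumed) | True use, fasted vs fed | True gap | Displayed, fasted vs fed | Displayed gap |
|---|---|---|---|---|
| 100% | 58.3% vs 33.3% | 25 points | 84.5% vs 80.9% | about 3.5 points |
| 50% | 29.2% vs 16.7% | 12.5 points | 54.0% vs 50.6% | about 3.3 points |
| 25% | 14.6% vs 8.3% | about 6 points | 30.3% vs 28.2% | about 2 points |

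The displayed level rises well above the true level because each column gathers use from three periods. The gap shrinks because columns share most of their subjects' other periods.

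**The case against.** The strongest reply is that little is lost. Intake times and start dates are recorded. AE records hold onset, end and any treatment required (Protocol 5.2.6.2.1), and each headache has its onset relative to dosing (Protocol 6.2.2). All individual values are listed (SAP 7). With 24 subjects and doses at least 17 days apart, a reader can trace a remedy to the preceding dose. Headache frequency and maximum intensity are tabulated by actual treatment (SAP 7.8.1). AEs that lead to significant concomitant therapy fall into a class with its own table.

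Most of this stands, and it limits the point to the summary. A reader might infer that remedies cannot be linked to treatment at all, or that a food-related difference in headache would be hidden. The data and the AE tables contradict both. A reader might also infer that co-medication could distort the PK comparison unnoticed. The documents do not support that either: restricted medication is a relevant deviation (Protocol 7.3), prohibited medication is a deviation category that can lead to exclusion from the PK set (SAP Table 6.2: 1), and no PK estimate uses this table.

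The percentages are open to fair criticism. The documents give no share of headaches treated, and Protocol 4.2.2.1 in principle allows no concomitant therapy, so universal treatment is unlikely. The earlier rates come from the first formulation and are applied here to the second. Under the sequence reading these percentages do not arise.

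What the reply does not supply is a by-treatment summary of use. In SAP 7.8.1, whether therapy was required appears only as a criterion for collapsing AE records. The separate table covers only therapy judged significant at a review meeting. Listings are sorted by sequence.

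SAP 7.8.1 also says of headache that "further information about the duration of headache, location, characteristics, and signs and symptoms were recorded". One might ask for duration to be split by receipt of therapy. That split conditions on a decision made after dosing that probably follows severity, and with 14 to 16 exposures per treatment the cells would be very small. It is not part of this point.

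**Conclusion.** The point holds as a reporting correction of low severity. As written, the planned summary of concomitant therapy cannot attribute use to the preceding formulation and food state under either reading of treatment group. This follows from the design and the sentence in Protocol 7.3.4 alone, and needs no assumption about how often remedies are used.

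The size of the distortion is not known. The illustrated shrinkage, from 25 points to about 3.5 or from 12.5 to about 3.3, depends on assumed shares treated, independence between periods, and earlier rates carried over to a different formulation. It shows the direction of the effect and is not a forecast. The primary and secondary PK analyses and the AE tables by treatment are unaffected.

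**What to change.** In Protocol 7.3.4 and SAP 7.2, replace the rule for therapies started after first dosing. Assign each one, by its recorded start date and, on study days, its intake time, to the on-treatment phase of SAP Table 6.1: 2 in which it started. Tabulate subjects with any use by treatment A to E, with the subjects exposed to that treatment as the denominator. Add concomitant therapy to the scope of Table 6.1: 2. Keep the period-free display for previous therapies only.

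If the protocol is not amended, SAP Section 4 can record the change, as it does for follow-up AEs.

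The cost is a few lines of SAP text and one reprogrammed table. Assignment by start needs no new data. The rule should not depend on stop times, because the documents do not say that these are recorded.

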#### **7.4 INTERIM ANALYSES**

No interim analysis is planned.

#### **7.5 HANDLING OF MISSING DATA**

##### **7.5.1 Safety**

It is not planned to impute missing values for safety parameters.

##### **7.5.2 Pharmacokinetics**

Handling of missing PK data will be performed according to the relevant Corporate Procedure ([001-MCS-36-472](#)).

PK parameters that cannot be reasonably calculated based on the available drug concentration-time data will not be imputed.

#### **7.6 RANDOMISATION**

Subjects will be randomised to one of the 12 treatment sequences in a 1:1:1:1:1:1:1:1:1:1:1:1 ratio. The block size will be documented in the CTR.

The sponsor will arrange for the randomisation as well as packaging and labelling of trial medication. The randomisation list will be generated using a validated system that uses a pseudo-random number generator and a supplied seed number so that the resulting allocation is both reproducible and non-predictable.

The randomisation list will contain additional blocks to allow for subject replacement (refer to [Section 3.3.5](#)).

#### **7.7 DETERMINATION OF SAMPLE SIZE**

It is planned to enter a total of 24 subjects in the trial to have at least 20 evaluable subjects, because this sample size is considered sufficient to achieve the aims of this exploratory trial. With this sample size, the following precision in estimating the ratio of geometric means (test/reference) can be expected with 95% probability. Precision is defined as the ratio of upper CI limit to the relative BA estimate. Note that the precision is independent of the actual ratio of geometric means.

Proprietary confidential information © 2019 Boehringer Ingelheim International GmbH or one or more of its affiliated companies

As shown in [Section 3.1](#) the trial design is an incomplete crossover with 5 treatments, 12 sequences and 3 periods. To ensure optimal statistical properties, the trial was initially designed in a balanced manner with 10 sequences (see Blocks 1-10 in [Section 3.1](#)). The required sample size for a balanced incomplete crossover design is given by  $n = \frac{M \times s \times p}{t \times \lambda}$ , where M is the sample size for the corresponding complete crossover design with s sequences, t treatments and p periods and  $\lambda$  shows how many times any given pair of treatments (e.g. A and B) appears in the sequences. For a  $5 \times 10 \times 3$ -balanced incomplete crossover, the required sample size is therefore  $n=2M$ . This means that the precision for this design with 20 subjects will be equivalent to the precision of a complete crossover design with 10 subjects (e.g.  $5 \times 10 \times 5$ ). For a given set of parameters, the number of subjects required for a complete crossover is the same to a first approximation regardless of its order (higher order complete crossovers have slightly higher power due to increased degrees of freedom). Therefore, a 20-subject  $5 \times 10 \times 3$  design is similar to (but slightly more powerful than) a 10-subject  $2 \times 2 \times 2$ , and this standard, simpler, design will therefore be used to estimate properties of the more complex design. The two additional blocks (CBA and AED) presented in [Section 3.1](#) are considered to provide additional data in favour of planned comparisons.

## **8. INFORMED CONSENT, TRIAL RECORDS, DATA PROTECTION, PUBLICATION POLICY, AND ADMINISTRATIVE STRUCTURE**

The trial will be carried out in compliance with the protocol, the ethical principles laid down in the Declaration of Helsinki, in accordance with the ICH Harmonized Guideline for Good Clinical Practice (GCP), relevant BI Standard Operating Procedures (SOPs), the EU regulation 536/2014, and other relevant regulations. Investigators and site staff must adhere to these principles.

Standard medical care (prophylactic, diagnostic, and therapeutic procedures) remains the responsibility of the subject's treating physician.

The investigator will inform the sponsor immediately of any urgent safety measures taken to protect the trial subjects against any immediate hazard, as well as of any serious breaches of the protocol or of ICH GCP.

The Boehringer Ingelheim transparency and publication policy can be found on the following web page: [trials.boehringer-ingelheim.com](http://trials.boehringer-ingelheim.com). The rights of the investigator and of the sponsor with regard to publication of the results of this trial are described in the investigator contract. As a general rule, no trial results should be published prior to archiving of the CTR.

The terms and conditions of the insurance coverage are made available to the investigator and the subjects, and are stored in the ISF.

